APPENDIX B: Lymphedema Quality of Life Survey

Lymphoedema Quality of Life Study (LYMQOL) LEG

If any of the items are not applicable to you, please write N/A in the relevant answer box(es).

(1) Has your swollen leg(s) affected:

	Not at all	A little	Quite a bit	A lot
a) your walking				
b) your ability to go up and down stairs				
c) your ability to bend, e.g. to tie shoelaces or cut toenails				
d) your ability to kneel				
e) your ability to stand				
f) your ability to get into/out of a car				
g) Your ability to get on/of public transport, e.g. trains/buses				
h) your ability to get up from a chair				
i) your ability to drive a car				
j) your occupation				
k) your ability to do housework				

(2) Does the swelling affect your leisure activities/social life?

Please give example(s) of this.

.....

(3) How much do you have to depend on other people?

(4) How much do you feel the swelling affects your appearance?

(5) How much difficulty do you have finding clothes to fit?

(6) How much difficulty do you have finding clothes you would like to wear?

(7) Do you have difficulty finding shoes to fit?

(8) Do you have difficulty finding socks/tights/stockings to fit?

(9) Does the swelling affect how you feel about yourself?

(10) Does it affect your relationship with your partner?

(11) Does it affect your relationships with other people?

(12) Does your lymphoedema cause you pain?

If so, do you have pain in the foot/feet

leg/legs

hip(s)

back

elsewhere — if so, where?

(13) Do you have any numbness in your swollen leg(s)?

(14) Do you have any feelings of 'pins and needles' or tingling in your swollen leg(s)?

(15) Does (do) your swollen leg(s) feel weak?

(16) Does (do) your swollen leg(s) feel heavy?

(17) Does (do) your swollen foot (feet) feel 'old'?

(18) Have you had any leakage of fluid from your leg(s)?

In the past week

(19) Have you had trouble sleeping?

(20) Have you had difficulty concentrating on things, e.g. reading?

(21) Have you felt tense?

(22) Have you felt worried?

(23) Have you felt irritable?

(24) Have you felt depressed?

(25) Overall, how would you rate your quality of life at present? Please mark your score on the following scale:

Poor	0	1	2	3	4	5	6	7	8	9	10	Excellent
------	---	---	---	---	---	---	---	---	---	---	----	-----------

Lymphedema Quality of Life Scoring System

LYMQOL ARM-Scoring System Lymphoedema Quality of Life Tool

The score for the individual responses are given below. If the item is not scored and left blank or not applicable this is scored with a 0. Domain totals are calculated by adding the individual scores and dividing the total by the number of questions answered. (If >50% of questions per domain are not answered this cannot be calculated and =0).

The four domains and their corresponding questions are: Function 1 (a-h), 2, 3;

Appearance 4, 5, 6, 7, 8; Symptoms 9, 10, 11, 12, 13, 14; and Mood 15, 16, 17, 18, 19, 20.

Overall quality of life (Q21) is scored as the value marked by the patient, between 0-10.

(1) How much does your swollen arm affect the following daily activities?

	Not at all	A little	Quite a bit	A lot
a) occupation	1	2	3	4
b) housework	1	2	3	4
c) combing hair	1	2	3	4
d) dressing	1	2	3	4
e) writing	1	2	3	4
f) eating	1	2	3	4
g) washing	1	2	3	4
h) cleaning teeth	1	2	3	4

(2) How much does it affect your leisure activities/social life?

1 2 3 4

Please give example(s) of this.

(3) How much do you have to depend on other people?

1 2 3 4

(4) How much do you feel the swelling affects your appearance?

1 2 3 4

(5) How much difficulty do you have finding clothes to fit?

1 2 3 4

(6) How much difficulty do you have finding clothes you would like to wear?

1 2 3 4

(7) Does the swelling affect how you feel about yourself?

1 2 3 4

(8) Does it affect your relationships with other people?

1 2 3 4

(9) Does your lymphoedema cause you pain?

1 2 3 4

(10) Do you have any numbness in your swollen arm?

1 2 3 4

(11) Do you have any feelings of 'pins and needles' or tingling in your swollen arm?

1 2 3 4

(12) Does your swollen arm feel weak?

1 2 3 4

(13) Does your swollen arm feel heavy?

1 2 3 4

(14) Do you feel tired?

1 2 3 4

In the past week

1 2 3 4

(15) Have you had trouble sleeping?

1 2 3 4

(16) Have you had difficulty concentrating on things, e.g. reading?

1 2 3 4

(17) Have you felt tense?

1 2 3 4

(18) Have you felt worried?

1 2 3 4

(19) Have you felt irritable?

1 2 3 4

(20) Have you felt depressed?

1 2 3 4

(21) (24) Overall, how would you rate your quality of life at present?

Please mark your score on the following scale:

1 2 3 4

Poor	0	1	2	3	4	5	6	7	8	9	10	Excellent
------	---	---	---	---	---	---	---	---	---	---	----	-----------

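### Appendix B prints the leg version of the LymQOL in an arm-lymphedema trial, and its arm scoring key gives a mostly blank domain a 0, better than the best possible answer of 1

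*Combined protocol and SAP*

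**What the plan says.** Section 3.1 admits only patients with upper-limb lymphedema after breast cancer treatment, and section 10.3.1.1 repeats this for the LymQOL analysis. Change in LymQOL is an exploratory objective (section 1.3).

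Section 10.3.1.2 scores answers from 1 to 4, higher being more severe. It defines change as the Month 12 aggregate minus the baseline aggregate, so a negative value is improvement, and it takes baseline as the average of the two qualifying screening visits.

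Appendix B opens with a form headed "Lymphoedema Quality of Life Study (LYMQOL) LEG". Its items concern walking, stairs, kneeling, shoes and socks, and it invites patients to write N/A where an item does not apply. Next comes "LYMQOL ARM-Scoring System Lymphoedema Quality of Life Tool", followed by the arm items with their response values. That key contains three scoring rules:

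- Single items: "If the item is not scored and left blank or not applicable this is scored with a 0".
- Domains: "Domain totals are calculated by adding the individual scores and dividing the total by the number of questions answered".
- Mostly blank domains: "If >50% of questions per domain are not answered this cannot be calculated and =0".

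The key assigns items 1a-h, 2 and 3 to Function, and the rest as follows: "Appearance 4, 5, 6, 7, 8; Symptoms 9, 10, 11, 12, 13, 14; and Mood 15, 16, 17, 18, 19, 20". Item 21 is overall quality of life, scored 0 to 10.

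**The concern.** There are two separate faults.

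First, the only respondent-style form in the appendix is for the wrong limb. Nothing in the body text says that patients receive it, and it may be a filing error. If a site did use it, the arm key would score many answers in the wrong domain. Section 12.6.1 plans to add three subsites, which would work from the same protocol.

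Second, the value given to an uncalculable domain lies outside the 1 to 4 range, on the favorable side. At Month 12, not answering reads as improvement. At a screening visit it lowers the baseline and reads as later worsening. LymQOL is the only patient-reported outcome listed, so this is where a reader will look for the patient's view of benefit.

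A smaller gap is that sections 10.3.1, 10.3.1.2 and 12.5.2 refer to an aggregate score without saying how the four domains form it. They also do not say that the 0 to 10 overall item, on which higher is better, is kept out of it.

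**Working it through.** **Leg form against arm key.** The leg form has items 1a-k (11) and 2-25 (24), which makes 35. The arm key covers 1a-h and 2-21, which is 8 + 20 = 28. If leg answers were scored with the arm key:

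| Arm key | Leg items that would land there |
|---|---|
| Symptoms (9-14) | 9-11 ask about self-image and relationships: 3 of 6 misplaced |
| Mood (15-20) | 15-18 ask about weakness, heaviness, foot sensation and fluid leakage: 4 of 6 misplaced |
| Item 21, overall quality of life, 0-10 | Feeling tense |
| Not scored | 1i, 1j, 1k and 22-25: 35 - 28 = 7 items, including the real overall item |

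**When the zero applies (arm key).** The smallest number of unanswered items above 50% is:

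| Domain | Items | Unanswered items that trigger the 0 |
|---|---|---|
| Function | 10 | 6 |
| Appearance | 5 | 3 |
| Symptoms | 6 | 4 |
| Mood | 6 | 4 |

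Up to the 50% limit the divisor is the number of questions answered, so the item-level 0 does no harm to the domain mean. A patient who answers 4 to three of the six Symptoms items scores 12/3 = 4.0. With one more item blank, the domain score becomes 0. Any calculable domain lies between 1.0 and 4.0, so 0 is a full point better than the best attainable score.

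**Size of the effect.** The documents define no aggregate and give no LymQOL scores. I assume that the aggregate is the mean of the four domains, that the baseline b is the same in each domain, and that b lies anywhere from 1 to 4. The patient is truly unchanged.

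One domain zeroed at Month 12: aggregate = 3b/4, so change = 3b/4 - b = -b/4. The best genuine change is 1 - b.

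One domain zeroed at one of the two screening visits: baseline = (b + 0.75b)/2 = 0.875b, so change = +0.125b.

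The arm-mean shift from one such patient is the change divided by 12 (control) or 48 (BioBridge), the completer numbers in section 12.6.2.

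| | b = 1 | b = 2.5 | b = 4 |
|---|---|---|---|
| Zero at Month 12: patient's change | -0.25 | -0.625 | -1.0 |
| Best genuine change | 0 | -1.5 | -3.0 |
| Shift in mean of 12 controls | -0.021 | -0.052 | -0.083 |
| Shift in mean of 48 BioBridge | -0.005 | -0.013 | -0.021 |
| Zero at one screening visit: patient's change | +0.125 | +0.3125 | +0.5 |
| Shift in mean of 12 controls | +0.010 | +0.026 | +0.042 |
| Shift in mean of 48 BioBridge | +0.003 | +0.007 | +0.010 |

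At b = 2.5 the spurious improvement is 0.625/1.5 = 42% of the largest genuine one. It exceeds the largest genuine improvement only when b/4 > b - 1, that is, when b < 4/3 = 1.33. If the aggregate were the sum of the domains, every figure in the table would be four times as large and the 42% would not change.

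**The case against.** The leg page has no demonstrated consequence. The full arm item list and arm domain map are printed directly after it, and staff would have to hand arm patients a form about walking and shoes and then score it with a key headed ARM. That stands: the item mapping above shows what would happen if the page were used, not what will happen.

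On the zero, a domain that cannot be calculated is arguably not a score at all, and 0 may be only a placeholder code. The item-level 0 in the same paragraph clearly works that way. However, the item-level 0 is neutralized by the divisor, whereas nothing neutralizes the domain-level 0. An analyst following the text would carry it into the aggregate.

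The N/A invitation appears only on the leg page, although the arm key also mentions items that are not applicable. N/A answers matter only if they count as unanswered towards the 50% limit, which the key does not settle.

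The remaining objections concern weight, and they stand. The endpoint is exploratory, most of a domain must be blank on a survey completed at study visits, and nothing in the documents suggests that blanks will differ by arm. The zero rule may also belong to the published instrument, which cannot be checked here, but the trial can still set its own analysis rule.

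**Conclusion.** The concern holds on both counts. The leg form is the wrong page for this trial, possibly through misfiling only. The zero rule is wrong as written, because it scores a mostly blank domain better than the best possible answer and no analysis text corrects this.

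On the stated assumptions, the distortion is modest for an arm mean but can be large for a single patient, and one affected control counts four times as much as one affected BioBridge patient (48/12). Without a difference in blanks between arms, the result is distorted within-arm change and added noise, not a biased comparison. The primary and secondary analyses and the sample size are not affected. The correction is worth making because it costs almost nothing and protects the trial's only patient-reported outcome.

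**What to change.** 1. Replace the leg page in Appendix B with the arm questionnaire, whose items are already worded in the scoring section.
2. Set a domain with more than 50% of items unanswered to missing, not 0. If the zero belongs to the published key and must stay on the form, state the set-to-missing rule in section 10.3.1.2 as the trial's analysis rule. For baseline, where a domain is missing at one screening visit, use the other visit.
3. Say in the same section whether N/A counts as unanswered, how the aggregate is formed from the four domains, what happens to it when a domain is missing, and that the 0 to 10 overall item is reported separately.

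The cost is one appendix page and a few sentences in section 10.3.1.2. There is no added patient burden and no effect on the primary or secondary analyses.
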